11.1. Adrenal insufficiency

Signs and symptoms of adrenal insufficiency and over treatment will be summarised by feeder study and previous treatment, including total column, and visit (including an overall summary over the study treatment period). A listing of all signs and symptoms of adrenal insufficiency and over treatment will be produced flagging any significant findings and significant findings related to under/over replacement of steroid.

11.2. Adverse events

All AEs, in terms of MedDRA system organ class (SOC) and preferred term (PT), will be listed and summarised descriptively by count (n) and percentage (%) by overall DIUR-006 study, feeder study and previous treatment. For the purpose of the clinical study report, only AEs up to 30 days after the end of the study or early withdrawal visit will be included in summaries. Any AE occurring before the first dose of Chronocort® (in the evening of the baseline visit) will be included in listings but not summaries, unless there is an increase in severity occurring after the start of treatment. Similarly, any AE with a start date after 30 days following the end of the study or early withdrawal will be listed but not summarised.

All reported AEs will be listed along with the study day of onset, resolution, duration, seriousness, severity, action taken with study drug, relationship to study drug, treatments administered and outcome. Any AE occurring within 28 days post COVID-19 vaccination shall be flagged on the listing as occurring within the immediate period post-vaccination.

A separate listing will be produced, including all the COVID-19 related AEs with an onset date on or after 11th March 2020 (start date of the pandemic according to WHO), based on the MedDRA COVID-19 related new terms spreadsheet.

Frequencies and percentages of subjects reporting each PT will be presented (i.e. multiple events per subject will not be accounted for). Where severity is displayed, if a subject has more than one AE of the same term, the maximum severity will be used.

An overview table of AEs displaying the number of AEs by overall DIUR-006 study, feeder study and previous treatment as well as the number and percent of subjects with the following categories will be produced:

- Any AE
- Any AE causally related to IMP
- Any AE leading to sick day rules
- Any AE leading to sick day rules causally related to IMP
- Any AE leading to adrenal crisis
- Any AE leading to adrenal crisis causally related to IMP
- Any AE of unexpected therapeutic benefit
- Any AE of unexpected therapeutic benefit causally related to IMP
- Any AE leading to death
- Any AE leading to death causally related to IMP

- Any AE leading to discontinuation
- Any AE leading to discontinuation causally related to IMP
- Any SAE
- Any SAE causally related to IMP
- Any SAE leading to discontinuation
- Any SAE leading to discontinuation causally related to IMP
- Any severe AE
- Any severe AE that is causally related to Chronocort
- Any AE associated with a dose increase
- Any AE associated with a dose increase and causally related to Chronocort
- Any AE associated with a dose decrease
- Any AE associated with a dose decrease and causally related to Chronocort
- Any AE associated with a dose interruption
- Any AE associated with a dose interruption and causally related to Chronocort.

The number and percent of subjects experiencing each AE will be summarised by overall DIUR-006 study, feeder study, previous treatment, SOC and PT for the following:

- All AEs
- All serious adverse events (SAEs)
- · SAEs with outcome of death
- AEs leading to discontinuation of study treatment
- SAEs leading to discontinuation of study treatment

Separate summaries for AEs and SAEs will be created, split by the following:

- Causality (not related, related to the investigational medicinal product (IMP), related to sick
 day medication, related to an interaction between IMP and sick day medication, related to
 either IMP or sick day medication)
- Action taken (dose unchanged, dose increased, dose decreased, drug interrupted, drug withdrawn)
- Outcome (Resolved, resolved with sequelae, resolving, not resolved, unknown, fatal)
- By severity (Mild, moderate, severe)

Tables of most common AEs (>10% of subjects overall) and common SAEs (>1% of subjects overall), will be summarised by PT, by decreasing frequency. These thresholds may be adjusted either upwards or downwards at the Data Review Meeting, depending on the actual number of subjects with AEs.

Version: 6.0 12 July 2022

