Study DIUR-004 was an open-label, randomised, single dose, 3-period, crossover study in 18 healthy male volunteers that was designed to assess the impact of food on the PK of Chronocort®. The study also evaluated the relative bioavailability of Chronocort® and immediate release hydrocortisone in the fasted state to support dosing in clinical practice. The results of this study showed that whilst extent of absorption of Chronocort® is unaffected, Tmax is delayed by approximately 2 hours, and Cmax is reduced by approximately 20% after food. Thus it is recommended that the morning dose of Chronocort® is taken on an empty stomach at least 1 hour before a meal and the evening dose should be taken at least 2 hours after the last meal of the day. From a safety perspective, one subject had mild AEs of epigastric pain and shortness of breath that were considered not related to the study drug (both were considered related to dexamethasone administration). Both events commenced together more than 4 days after dosing and lasted 11 days. The subject was withdrawn from the study as a result of these events. A second subject reported an AE of headache, but this occurred 14 days pre-dose and lasted 1.5 hours and there was no causal relationship with the study drug.

Version: 20.0 – 16 Jun 2022 Page **19** of **96** 

Study DIUR-005 was an open-label, randomised, parallel arm, Phase III study that was designed to evaluate the efficacy, safety and tolerability of Chronocort® compared with standard glucocorticoid replacement therapy in the treatment of subjects with CAH. This study has just completed and the results have been reported. The primary endpoint of the study (change from baseline to Week 24 of the natural logarithm of the mean of the 24-hour standard deviation score [SDS] profile for the natural logarithm of 17-OHP) was not met. However, secondary and post-hoc analyses were consistent in showing improved control of 17-OHP with Chronocort® treatment. In addition, a reduced incidence of adrenal crises, fewer occurrences of the use of sick day rules for AEs, and an increased incidence of therapeutic benefits (fatigue reduction, improvement of hirsutes, menstrual benefits) were reported following Chronocort® treatment.

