## 12 Adverse Events and Toxicity Management

## 12.1 Adverse Event Definition

An AE is defined as (21CFR312.32): "Any untoward medical occurrence associated with the use of a drug in humans, whether or not considered drug related." An AE can therefore be any unfavourable and unintended sign (including an abnormal laboratory finding), symptom, or disease temporally associated with the use of a medicinal (investigational) product, whether or not related to the medicinal (investigational) product. This includes any newly occurring event or previous condition that has increased in severity or frequency since the administration of study drug.

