Investigators may be asked for additional information for any report of an SAE. An SAE form indicated as a follow-up report with attached documents (if necessary) should be forwarded to the sponsor/designee as soon as the additional information is available. The sponsor will submit to the Regulatory Authority(ies) all safety updates and periodic reports, as required by applicable regulatory requirement(s).

Some of the AEs likely to occur in subjects with CAH, are of special interest, and whilst they may not be defined as SAEs, they will be reported in the same manner in order to capture the data in real time, together with additional data, if this should be required. However these events will not be reported to the Regulatory Authorities unless they are defined as SAEs. These events will include, but not be limited to, Addisonian crisis and events causing implementation of 'sick day rules'.

Addisonian or adrenal crisis is defined as follows (based on Allolio 2015):

• (A): Major impairment of general health with at least two of the following signs/symptoms:

Hypotension (systolic blood pressure <100 mmHg)

Nausea or vomiting

Severe fatigue

Fever

Somnolence

Hyponatraemia (<132 mmol/L) or hyperkalaemia (as judged by characteristic electrocardiogram [ECG] changes)

Hypoglycaemia

• (B): Parenteral glucocorticoid (hydrocortisone) administration followed by clinical improvement:

Grade 1: outpatient care only

Grade 2: hospital care (general ward)

Grade 3: admission to intensive care unit

Version: 20.0 – 16 Jun 2022 Page **47** of **96** 

Grade 4: death from adrenal crisis (with or without parenteral glucocorticoid administration)

In addition, some events may occur that represent an improvement in the subject's condition e.g. restoration of menses. These events are of special interest and should be recorded as AEs of special interest, clearly stating that the event is an improvement in the condition, and these events will be coded as 'Unexpected Therapeutic Effect'. Whilst these events are not SAEs, they should be reported in the same manner as SAEs in order to capture the data in real time, together with additional data, if this should be required. However these events will not be reported to the regulatory authorities as SAEs.

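### Improvements recorded as AEs are not kept out of the AE summaries, so the subject-level related-AE percentage and the AE breakdown tables mix benefits with harms

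*SAP*

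**What the plan says.** Protocol 12.9 covers events that are improvements and gives restoration of menses as the example. Such events "should be recorded as AEs of special interest, clearly stating that the event is an improvement in the condition". They share one code, Unexpected Therapeutic Effect. The section also says that they are not SAEs, although they follow the SAE reporting route. Protocol 12.1 defines an AE as "Any untoward medical occurrence associated with the use of a drug in humans, whether or not considered drug related".

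Occurrence of AEs is the fourth of six components of the primary safety endpoint (Protocol 7.1 and 13.3.1, SAP 2.2.1). SAP 11.2 sets the scope of the AE summaries: "All AEs, in terms of MedDRA system organ class (SOC) and preferred term (PT), will be listed and summarised descriptively". Two exclusions follow, both by timing. Events before the first dose are listed only, unless they worsen on treatment. Events starting more than 30 days after the end of study or early withdrawal are also listed only.

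The overview table in SAP 11.2 has a row for any benefit event and a row for "Any AE of unexpected therapeutic benefit causally related to IMP", in the same list as the any-AE and related-AE rows. SAP 11.3.3 and Protocol 13.6.1 add a separate table and listing of benefit events. Neither removes these events from the other tables, and SAP Appendix A plans no AE table without them.

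**The concern.** An improvement is not untoward, so counting it in an AE total conflicts with the protocol's own definition. If the plan is followed literally, a favourable effect raises the reported frequency of AEs. Where the investigator attributes it to Chronocort, it also raises the frequency of related AEs, and it meets the wording for an adverse drug reaction in Protocol 12.5.

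Such events are to be expected. Of the feeder study DIUR-005, Protocol 5.5 says that on Chronocort "an increased incidence of therapeutic benefits (fatigue reduction, improvement of hirsutes, menstrual benefits) were reported".

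Two further effects are possible. Unlike improvements pooled under one code could together look like a common adverse event. And because the tables are split by previous treatment, benefits may be counted unevenly between columns.

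**Working it through.** **Step 1: which outputs are affected.** Each output is set against the exclusion rules in SAP 11.2.

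| Output | Benefit events included as written? | Can a reader recover the harm-only figure? |
|---|---|---|
| Any AE, % of subjects | Yes | Not by subtraction: one subject can have both a harm and a benefit |
| Any related AE, % of subjects | Yes, if judged related | Not by subtraction, same reason |
| Event counts (overview; Table 14.3.1.2, episode level) | Yes | Yes: total minus the benefit row |
| SOC/PT table | Yes | The PT row is identifiable by its label; subject totals are not separable |
| Causality, severity, action, outcome | Yes | No benefit split planned; only by working through the listing |
| Most common AEs | Yes, if above 10% | The label is visible |
| SAE tables | No, since Protocol 12.9 says these events are not SAEs | Not needed |

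**Step 2: size for the related-AE percentage.** The documents state no AE, related-AE or benefit rate, so there is no figure to reproduce. Everything in this step rests on assumed rates.

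Let p be the proportion of subjects with a true related AE and b the proportion with a benefit judged related. A subject counts once (Protocol synopsis: at least one AE), so the reported rate is p + b − P(both). It lies between max(p, b) and min(1, p + b). Under independence it is p + b(1 − p). With p = 0.15:

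- b = 0.05: 0.15 + 0.05 × 0.85 = 0.1925. Limits 0.15 to 0.20.
- b = 0.20: 0.15 + 0.20 × 0.85 = 0.32. Limits 0.20 to 0.35.

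Full overlap, with every benefit subject also having a true related AE, leaves the 15% unchanged. That is possible only while b does not exceed p. At b = 0.20 the reported rate cannot be below 20%.

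**Step 3: other assumed rates, at the maximum enrolment of 16 + 122 = 138.** Each cell runs from greatest overlap to none.

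| Harm-only subjects | 7 benefit subjects | 14 benefit subjects | 28 benefit subjects |
|---|---|---|---|
| Related AE: 14 (10.1%) | 10.1–15.2% | 10.1–20.3% | 20.3–30.4% |
| Related AE: 41 (29.7%) | 29.7–34.8% | 29.7–39.9% | 29.7–50.0% |
| Any AE: 124 (89.9%) | 89.9–94.9% | 89.9–100% | 89.9–100% |

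Under independence the any-AE row becomes 90.4%, 90.9% and 91.9%, a shift of about 2 points at most. The middle row becomes 33.3%, 36.8% and 44.0%.

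**Step 4: most-common-AE table.** 10% of 138 is 13.8, so 14 subjects (10.1%) under one preferred term would pass the threshold. SAP 11.2 allows the Data Review Meeting to change it.

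**Step 5: columns by previous treatment.** Protocol 13.6.1 counts events from the first Chronocort dose in this study. Subjects continuing from the DIUR-005 Chronocort arm had 24 weeks in which to improve before that point. Subjects from the standard-GC arm did not. The third column, non-study GC (SAP Table 1), holds DIUR-003 and DIUR-005 gap subjects. DIUR-003 subjects had already been studied on Chronocort over 6 months (Protocol 5.5), and gap subjects are not restricted to the standard-therapy arm. Only the standard-GC versus continuing-Chronocort contrast is reasonably clear.

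**The case against.** The strongest defence is that nothing is hidden and nothing is tested. The events carry a code that no one would mistake for a harm. They have two overview rows, their own table and their own listing, and event counts can be corrected from the overview. The study is descriptive, without formal comparisons or a sample size calculation, so no decision rule depends on the figure. Every rate used to size the effect is assumed.

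Most of this stands, and it limits the point. It does not answer it, because the subject-level percentages and the breakdown tables cannot be corrected by subtraction.

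There is also a fair objection to simply dropping the events. Interim analyses used the same endpoints for regulatory review, and the version 12.0 entry in Protocol Appendix 9 indicates that some had taken place. A filter applied only to the final report would break comparability, and deleting the overview rows would remove existing disclosure. The fix has to allow for both.

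A reader might infer several stronger things that the documents do not support:

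- That the primary safety endpoint as a whole counts benefits as harms. Five of the six components (symptoms, sick-day rules, adrenal crises, laboratory measures, and vital signs with body measurements) are untouched.
- That improvements are by their nature judged drug-related. Protocol 12.5 offers a not-related category, and the SAP has separate rows for all benefit events and for related ones.
- That SAE totals are inflated because the SAE reporting route is used. Protocol 12.9 says that these events are not SAEs.
- That everyone starting Chronocort in this study can newly improve, unlike continuing subjects. Step 5 shows why this fails for the non-study-GC column.

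**Conclusion.** Wrong as written, with limited scope. Following SAP 11.2 literally puts recorded improvements into one of the six primary safety components, against the protocol's own AE definition. The figures that matter are the percentage of subjects with a related AE and the AE tables by preferred term, causality, severity, action and outcome. The any-AE percentage probably moves little if nearly all subjects have some AE over up to 5.5 years, which is itself an assumption.

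The size is unknown. The 19% to 32% illustration rests on an assumed 15% true related-AE rate, an assumed 5% to 20% related-benefit rate, and independence. It shrinks with overlap, to no change where every benefit subject also has a true related AE. A distorted comparison by previous treatment is plausible mainly between the standard-GC and continuing-Chronocort columns, and that comparison is never tested.

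**What to change.** In SAP 11.2, state that events recorded as unexpected therapeutic benefit are excluded from the any-AE and related-AE totals and from the AE tables by SOC/PT, causality, severity, action taken and outcome, as well as from the most-common-AE table. Keep them in all listings, in the SAP 11.3.3 table, and in the overview table as a separately labelled block that does not feed the totals.

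Also show the any-AE and related-AE totals with these events included, so that the final report stays comparable with earlier interim analyses.

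The cost is a short addition to the SAP, a filter in the AE programs, two extra rows and a footnote. The events are already identified for SAP 11.3.3, so no new data are needed.

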AEs will be coded using the latest version of the MedDRA drug dictionary. Data will be summarised using preferred term (PT) and primary system organ class (SOC). Only treatment-emergent AEs, i.e. AEs with an onset at or after the first administration of Chronocort® in this study, will be presented in summary tables. Where changes in severity are recorded in the eCRF, the most severe incidence of the AE will be reported in the tables. Rates will be calculated as the proportion of subjects with at least one AE related to the number of subjects treated in each treatment group. Frequency tables will be provided concerning severity and drug relationship.

Summary vital signs changes from baseline will be presented in tabular form using standard summary statistics.

Absolute and change from baseline in safety laboratory variables will be summarised over time using standard summary statistics at each time point. Shift tables from baseline to the maximum and minimum on-treatment values will be presented. The 3 x 3 cross tabulations (from low, normal and high to low, normal and high) will be presented. Values outside the normal ranges (provided with the laboratory report), will be flagged in the subject data listings.

Version: 20.0 – 16 Jun 2022 Page **8** of **96** 

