#### 13.1 Conventions and Methods

#### 13.1.1 Summary Tables, Listings and Figures

The standard summary statistics for continuous baseline and outcome variables are: N, mean, standard deviation (SD), median, quartiles, minimum and maximum. The standard summary statistics for categorical baseline and outcome variables are: count and proportion (expressed as percentage). Geometric mean and coefficient of variation will also be presented for variables which will subsequently be log-transformed during the analysis.

Summary tables and figures will be supported by full subject listings.

Data will be summarised according to time since first dose of Chronocort® treatment (which may have been in the feeder study for study DIUR-005). Time slotting will be described in the SAP.

Safety and efficacy parameters will be explored based on previous treatment in the feeder study and by previous standard therapy. Exploratory analyses will also be undertaken to assess the relationship between disease control and the proportion of daily dose given at night. Further details will be provided in the SAP.

For subjects who re-enter the study post-pregnancy, data collected during the post-pregnancy phase will be listed only. Only data up to the time of first study withdrawal will be included in summary tables and figures. Individual subject profiles will be created to support discussion of data from this small subset of subjects in the clinical study report.

Disruptions due to the COVID-19 pandemic will be summarised by feeder study and previous treatment. The summary will include an overview of study visit or study medication disruptions due to the COVID-19 pandemic, as well as including whether the scheduled visit was delayed or scheduled assessments were not done. Detailed listings of study visit disruptions and study medication disruptions will be produced.

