#### 13.6 Efficacy and Safety Analyses

#### **13.6.1 Safety**

Signs and symptoms of adrenal insufficiency or over-treatment will be summarised over time. A listing of all signs and symptoms of adrenal insufficiency will be produced, flagging any significant findings as well as a listing of significant findings related to under/over replacement of steroid.

AEs will be coded using the latest version of the Medical Dictionary for Regulatory Activities (MedDRA). Data will be summarised using preferred term (PT) and primary system organ class (SOC). Only treatment-emergent AEs, i.e. AEs with an onset at or after the first administration of Chronocort®in this study and up to 30 days after the end of the study or the early withdrawal visit, will be presented in summary tables. Where changes in severity are recorded in the eCRF, the most severe incidence of the AE will be reported in the tables. Frequency tables will be provided concerning severity and drug relationship.

Each site will have a set of sick day rules where certain AEs will result in emergency hydrocortisone being taken. All AEs leading to use of "sick day rules" will be summarised (frequency and percentage of subjects) by SOC and PT. Use of sick day medication will be summarised.

All AEs leading to adrenal crises will be summarised (frequency and percentage of subjects) by SOC and PT.

Version: 20.0 – 16 Jun 2022 Page **52** of **96** 

All AEs of unexpected therapeutic benefit will be summarised (frequency and percentage of subjects) by PT, lower level term, and treatment group. There will be a separate listing showing details of all AEs of unexpected therapeutic benefit.

Absolute and change from baseline in safety laboratory variables will be summarised over time. Shift tables from baseline to the maximum and minimum on-treatment values will be presented. The 3 x 3 cross tabulations (from low, normal and high to low, normal and high) will be presented. Values outside the normal ranges will be flagged in the subject data listings.

Changes from baseline in vital signs data, weight, BMI, and waist circumference will be summarised over time. Abnormal findings in the physical examination will be tabulated by body system showing the frequency and percentage of subjects with an abnormal finding.

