2.2. Study endpoints

2.2.1. Primary endpoints

The primary endpoint is the safety of Chronocort® over time, assessed using but not limited to the following endpoints:

- 1. Signs and symptoms of adrenal insufficiency or over-treatment throughout the study.
- 2. Use of sick day rules throughout the study.
- 3. Occurrence of adrenal crises throughout the study.
- 4. Occurrence of AEs throughout the study.
- 5. Change from pre-Chronocort® baseline in safety laboratory assessments at each visit throughout the study.
- 6. Change from pre-Chronocort® baseline in vital signs (blood pressure [BP], heart rate, respiration rate, body temperature), weight, body mass index (BMI), and waist circumference at each visit throughout the study.

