7.1. General

Since all subjects participating in this trial will be receiving Chronocort®, there will be no formal treatment comparisons. Summaries over time will be produced for safety and efficacy parameters.

For subjects who re-enter the study post-pregnancy, all data collected at following re-entry will be included in the summaries and analyses. For these patients, the original date of first dose of randomized treatment will be used as the date of origin for the assignment of visit windows and the calculation of relative date/time information.

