9.3.1. Definition of permissible time windows

Actual study day will be calculated by:

• Date of assessment - Date of first dose + 1 (or Date of assessment - Date of first dose if the assessment is before the date of first dose).

Version: 6.0

Protocol No.: DIUR-006

However, due to the first dose being scheduled at 23:00h on the evening of the baseline assessment¹ (Visit 1), a window of +4 hours will be used so that if the time of first dose falls within the window,

the date of first dose will be considered to be the planned date of first dose. For example, if a subject takes their first dose at 01:00h the day after the baseline assessment, the date used for the calculation of study day will still be the day of the baseline assessment.

Vital signs, laboratory data, bone turnover markers, physical examinations (including weight, BMI and waist circumference), endocrine profile (17-OHP and A4), signs and symptoms of adrenal insufficiency, DEXA scans and QoL data will be summarised according to scheduled visit.

Please note that visits 2 and 3 are when specific assessments of 17-OHP, A4 and signs and symptoms of adrenal insufficiency are performed. Any extreme deviations between the actual study day of the scheduled visit and the target study day (see Table 7) will be discussed at the Data Review Meeting. A deviation will be considered extreme if more than +/- 3 weeks (+/- 21 days) from visit 2, +/- 4 weeks (+/- 28 days) from visit 3 and 4, or +/- 3 months (+/- 84 days) for visit 5 and onwards. If 2 or more visits (including unscheduled visits) occur within the same analysis window, then the visit closest to the target study day will be used in the descriptive summaries. In case of equidistant visits to the target study day, then the earliest visit will be used in the analyses. All visits will be displayed in the listings.

Table 7: Target study day for visit assessments

Visit number	Visit description	Target study day	Target study day range
Visit 0	Visit 0/Screening	-14 to -1	
Visit 1	Visit 1/Baseline	1	
Visit 2	Visit 2/Week 4	29	8-50
Visit 3	Visit 3/Week 12	85	57-113
Visit 4	Visit 4/Week 24	169	141-197
6-monthly visits from visit 5 onwards			
Visit 5	Visit 5/Month 12	365	281-449
Visit 6	Visit 6/Month 18	548	464-632
Visit 7	Visit 7/Month 24	730	646-814
Visit 8	Visit 8/Month 30	913	829-997
Visit 9	Visit 9/Month 36	1095	1011-1179

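### Adverse event, serious adverse event and sick-day tables have no split by time on Chronocort and no person-time, although the primary endpoint is safety over time

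*SAP*

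**What the plan says.** **Endpoint.** SAP 2.2.1, like Protocol 7.1 and 13.3.1, states: "The primary endpoint is the safety of Chronocort® over time, assessed using but not limited to the following endpoints". Use of sick day rules and occurrence of AEs are two of the six listed components, each to be assessed throughout the study.

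**General commitments on time.** Protocol 13.1.1: "Data will be summarised according to time since first dose of Chronocort® treatment", followed by "Time slotting will be described in the SAP". SAP 7.1, like Protocol 13.1.2: "Summaries over time will be produced for safety and efficacy parameters".

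**AE-specific text.** The protocol synopsis says: "Rates will be calculated as the proportion of subjects with at least one AE related to the number of subjects treated". For AEs leading to sick day rules, Protocol 13.6.1 says they "will be summarised (frequency and percentage of subjects) by SOC and PT". SAP 11.2 follows: "Frequencies and percentages of subjects reporting each PT will be presented (i.e. multiple events per subject will not be accounted for".

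**Time slots actually defined.** SAP 9.3.1 gives a list that begins with vital signs and laboratory data and ends: "signs and symptoms of adrenal insufficiency, DEXA scans and QoL data will be summarised according to scheduled visit". AEs and sick-day use are not on it.

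**Person-time.** SAP 11.3.2 plans a rate per 100 subject years for adrenal crises only, as one whole-study figure per group.

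**The concern.** In a long extension study, the safety question that the feeder studies could not answer is whether events become more or less common with longer treatment. The primary endpoint and the general statements point to that question. For two of the six primary components the planned output gives only totals over the whole study. Day of onset appears in the AE listing, so a trend could be worked out later. The time origin, risk set and cut-off for events would then be chosen after the data had been seen.

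**Working it through.** **1. Planned summaries of the six primary components (SAP 11 and Appendix A)**

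| Component | Planned summary | By time? | Person-time? |
|---|---|---|---|
| Signs and symptoms (11.1) | by visit, plus overall | yes | not needed |
| Sick day rules (11.3.1; Tables 14.3.5.1, 14.3.5.1.1) | n (%) by SOC/PT, route, medication | no | no |
| Adrenal crises (11.3.2; Tables 14.3.5.2.1, 14.3.5.2.2) | n (%), rate per 100 subject years | no | yes |
| AEs and SAEs (11.2; Tables 14.3.1.1 to 14.3.1.8 and SAE repeats) | n (%); event counts in the overview and in episode-level Table 14.3.1.2 | no | no |
| Laboratory (11.4) | by visit | yes | not needed |
| Vital signs, weight, waist (11.5) | by visit | yes | not needed |

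Exposure by group is tabulated separately (Table 14.1.8.1.1). A reader could therefore derive one crude study-wide AE rate per group, but no course over time.

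**2. Length of follow-up.** The synopsis gives August 2016 to February 2022, at most 5.5 years, with last entry on 31 October 2018. From 31 October 2018 to 28 February 2022 is 1216 days; 1216/365.25 = 3.33 years. Completers are therefore followed for about 3.3 to 5.5 years, with a midpoint of about 4.4.

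**3. What a whole-study percentage can show.** The documents give no event rates, so the rates here are assumed. With cumulative hazard H, the proportion ever affected is 1 − exp(−H). Over a common 4.4 years:

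- Flat, 0.20/year: H = 0.20 × 4.4 = 0.88.
- Early excess, 0.54 in year 1 then 0.10/year: H = 0.54 + 0.10 × 3.4 = 0.88.
- Late excess, 0.10/year then 0.54 in the last year: H = 0.10 × 3.4 + 0.54 = 0.88.

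Each gives 1 − exp(−0.88) = 58.5% and the same expected number of events.

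The equality depends on the common follow-up. Place the late excess at years 3.4 to 4.4, with 0.10/year afterwards:

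| Follow-up | Flat | Early excess | Late excess |
|---|---|---|---|
| 3.33 years | 48.6% | 53.8% | 28.3% |
| 4.4 years | 58.5% | 58.5% | 58.5% |
| 5.5 years | 66.7% | 62.8% | 62.8% |

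The percentages can therefore differ between courses, but one pooled percentage still does not show which course produced it.

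**4. Would a 12-month split be precise enough?** These are exact Poisson 95% intervals per 100 subject years for the first 12 months. The upper bound on person-time is 138 subject years.

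- 0.54/year: 75 events, 43 to 68.
- 0.20/year: 28 events, 14 to 29.
- 0.10/year: 14 events, 6 to 17.

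The 138 is not reached if time runs from the first continuous dose and immediate-entry Chronocort subjects join at their first DIUR-006 dose. Each then adds at most about 52 − 24 = 28 weeks to year 1. Their number is not in the documents. If it were 61 (half of 122, assumed), year 1 would hold 138 − 61 × 24/52 = 110 subject years, and 0.54/year would give about 59 events with an interval of about 41 to 69. Between 0 and 61 such subjects, the interval moves only from 43–68 to 41–69.

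DIUR-003 supplies at most 16 subjects. In one 12-month period, 3 events in 16 subject years give about 4 to 55, too wide to be useful. Over the whole study (16 × 3.33 = 53 to 16 × 5.5 = 88 subject years), a rate near 20 has an interval of about 10 to 37 (11 events) or 12 to 32 (18 events). Period splits are therefore informative only for the overall column.

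**The case against.** **The endpoint text distinguishes its components.** Items 1 to 4, which include AEs and sick day rules, are assessed throughout the study. Items 5 and 6, laboratory and vital signs, are assessed at each visit. Protocol 13.6.1 is similar: laboratory values, vital signs and signs and symptoms are summarised over time, while sick-day AEs and crises get frequency and percentage. The synopsis defines AE rates as proportions of subjects. This stands. A reader might infer that the SAP departs from the protocol or fails to deliver the primary endpoint, but the documents do not support that. The SAP carries out the specific text, and what remains is a tension with the general sentences, which make no exception for AEs.

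**Other views of safety exist.** Interim analyses repeat the tables at successive cut-offs, and the DSMB reviews safety data regularly. This helps a little, but cut-offs follow calendar date, not time on treatment.

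**A period table would not be a clean answer.** This also stands:

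- Visits at Weeks 4, 12 and 24, with calls between them, make ascertainment denser in the first six months. Later visits are 6-monthly, and the 3-monthly calls record spontaneously reported AEs (Protocol 11.1.9).
- Later periods overlap COVID-19 and remote visits (Protocol 11.11).
- Later periods hold only early enrollees and subjects still on study, and SAP 9.3.3 expects some to leave on commercialisation.
- There is no comparator.

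These are reasons to footnote the table and keep it descriptive. They do not favour whole-study totals, which carry the same distortions without showing them.

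**Conclusion.** The point holds as a gap between general commitments and specific tables. For AEs, SAEs and AEs leading to sick day rules, nothing planned shows the course with time on Chronocort, and only adrenal crises have person-time, also without a time split. That the planned tables would look identical for any rising, flat or falling course is a tempting inference, but too strong. Equality holds for courses matched on cumulative hazard over one common follow-up (58.5% at 4.4 years) and fails at 3.33 or 5.5 years. The supported statement is that the totals cannot identify the course.

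The gap is worth closing but does not invalidate the planned tables. The absence of a time split rests on the text alone. The numerical illustrations rest on assumed rates, Poisson counts, no dropout and the stated study dates; repeat events within subjects would widen the intervals.

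**What to change.** Keep all existing tables and amend SAP 11.2 and 11.3.1 as follows.

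1. **Add one descriptive table** for any AE, any SAE and AEs leading to sick day rules. In the overall column, by 12-month period, show subjects at risk, events, subject years and the rate per 100 subject years. Give a 95% interval that allows for repeat events, or an exact Poisson interval labelled as not allowing for them. Add one whole-study rate by feeder study and previous treatment, as already planned for adrenal crises.
2. **Define the clock.** Count from the first dose of continuous Chronocort, matching the pre-Chronocort baseline definition (Protocol 7.2). Immediate-entry Chronocort subjects enter the risk set at their first DIUR-006 dose. State openly that this restarts the clock for DIUR-003 and gap subjects, whereas Protocol 13.1.1 counts from the first Chronocort dose.
3. **Use one collection window for events and person-time**, after reconciling two conflicts. The end of AE collection is 30 days after the last dose, or the start of DIUR-015 dosing if sooner (Protocol Table 1, footnote 12), after the last or early withdrawal visit (Protocol 12.2), or after the end of the study or the early withdrawal visit (Protocol 13.6.1, SAP 11.2). Data after post-pregnancy re-entry are listed only (Protocol 13.1.1) or included in summaries (SAP 7.1).
4. **Footnote** the denser early ascertainment, the COVID-19 overlap and the selective later follow-up.
5. **Separately, and minor:** Protocol 12.5 has six causality categories and SAP 11.2 has five. Add the missing one, relation to medication from a previous Chronocort study.

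The cost is SAP wording and a little extra programming on data already collected. Rates in small groups will be imprecise.
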